13.4.1.2 Response Rate

Response rate will be defined and reported as outlined in Sections 11 and Section 13.5.2 below.

13.4.1.3 Pharmacodynamic Endpoints

Change in levels (between pre-treatment and post-treatment tumor biopsies) of proteins/mRNAs implicated in MAPK or BCL2 family signaling (e.g. phosphorylated ERK (P-ERK)), proliferation markers (Ki67), or apoptosis markers (Cleaved caspase-3) will be evaluated in paired tumor biopsies obtained. Results will be reported as a % increase or decrease in level of a given marker after treatment initiation (day 15 biopsy) relative to before treatment (pre-treatment biopsy). For example, the % increase or decrease in the H-score of P-ERK, Ki67, or Cleaved caspase-3 will be reported relative to the pre-treatment biopsy.

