9.1.2.2 Procedures and analysis

Given the potential effects of navitoclax on platelets and bleeding risk, platelet count and coagulation studies (INR, PTT) will be checked on the same day prior to any research biopsies performed while patient is taking study drugs. A platelet count of >50,000/m³ and an INR and PTT in the normal/acceptable range according to institutional guidelines will be required for a patient to undergo tumor biopsy.

Pre-treatment biopsies will be obtained between days -21 and -1 of treatment. When possible, it is preferred, but not required, that the pre-treatment biopsy be performed between days -7 and -1 of treatment in order to most accurately represent the baseline signaling activity prior to treatment. On-treatment biopsies will be obtained after ~2 weeks of combination dosing (day 22 +/- 7 days for Schedule A dosing, day 15 +/- 7 days for Schedule B or C dosing). Core biopsies of the same tumor lesion will be obtained at each time point. A minimum of one core will be formalin-fixed and paraffin-embedded, and a minimum of one core will be flash frozen. Both formalin-fixed paraffin-embedded and flash frozen tissue will be stored in the pathology department at the Massachusetts General Hospital.

Paired biopsies will be used to assess the pharmacodynamic response to therapy in patients treated with trametinib and navitoclax. Markers to be assessed will include proteins or mRNAs involved in MAPK or BCL2 family signaling (e.g. phospho-ERK, phospho-S6, or MAPK phosphatases such as DUSP6/MKP1) to evaluate pathway inhibition, markers of tumor cell proliferation (e.g. Ki67), and markers of apoptosis and cell death (e.g. Cleaved caspase-3).

These ancillary/exploratory analyses will be conducted in the Massachusetts General Hospital Molecular Pathology Biomarker Laboratory. For each patient, the change in marker level between the pre-treatment and on-treatment biopsies will indicate the effects of treatment on each marker. Results will be reported as a % increase or decrease in level of a given marker after treatment initiation (on-treatment biopsy) relative to before treatment (pre-treatment biopsy).

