13.1.2.3 Secondary Objective

• To evaluate the pharmacodynamic response to therapy in tumor biopsies (first 15 patients enrolled overall, minimum 4 patients biopsied in each of expansion cohorts 1, 2, and 3)

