13.1.2.4 Secondary Endpoints

• Pharmacodynamic Endpoints: Change in levels (between pre-treatment and day 15 tumor biopsies) of proteins/mRNAs implicated in MAPK or BCL2 family signaling, proliferation markers (Ki67), or apoptosis markers (Cleaved caspase-3)

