13.4.2 Secondary Endpoints for Part 2 (Phase 2)

13.4.2.1 Pharmacodynamic Endpoints

Change in levels (between pre-treatment and post treatment tumor biopsies) of proteins/mRNAs

NCI Protocol #: 9525

Version Date: July 22, 2022

implicated in MAPK or BCL2 family signaling (e.g. phosphorylated ERK (P-ERK)), proliferation markers (Ki67), or apoptosis markers (Cleaved caspase-3) will be evaluated in paired tumor biopsies obtained. Results will be reported as a % increase or decrease in level of a given marker after treatment initiation (post treatment biopsy) relative to before treatment (pretreatment biopsy). For example, the % increase or decrease in the H-score of P-ERK, Ki67, or Cleaved caspase-3 will be reported relative to the pre-treatment biopsy.

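### Percent change from the pre-treatment biopsy is the only stated pharmacodynamic scale; it has no value at a zero baseline, so it can lose or distort cleaved caspase-3 pairs

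*Combined protocol and SAP*

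**What the plan says.** Three places in the combined protocol and SAP set the reporting scale.

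- Section 13.4.1.3 (Part 1) states the rule, "Results will be reported as a % increase or decrease in level of a given marker after treatment initiation", and then gives the example: "the % increase or decrease in the H-score of P-ERK, Ki67, or Cleaved caspase-3 will be reported relative to the pre-treatment biopsy".
- Section 13.4.2.1 (Part 2) repeats it, again for "the % increase or decrease in the H-score of P-ERK, Ki67, or Cleaved caspase-3".
- Section 9.1.2.2 (correlative procedures) says the same in general terms: "Results will be reported as a % increase or decrease in level of a given marker".

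The endpoint lists in Sections 13.1.1.4 and 13.1.2.4 are looser. They speak only of a change in the levels of proteins or mRNAs and fix no scale.

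On numbers, Section 13.1.2.3 plans Part 2 biopsies in the "first 15 patients enrolled overall, minimum 4 patients biopsied in each of expansion cohorts 1, 2, and 3". Part 1 dose levels hold 3 patients, expanded to 6 after one dose-limiting toxicity (Section 5.1.1).

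The documents do not say what to do with a zero or near-zero baseline. They do not define the H-score, give any baseline values, or say whether pairs are summarised by a mean or a median. Sections 9.1.2.1 and 9.1.2.2 call these analyses ancillary or exploratory, and no test or decision rule is attached to them.

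**The concern.** Cleaved caspase-3 is the listed marker closest to the trial's rationale. Section 2.4 argues that MEK inhibition alone usually slows growth without killing cells, and that in preclinical tumours marked cell death appeared only with the combination. A patient whose tumour shows little apoptosis before treatment and clearly more on treatment would fit that rationale well. Percent change works worst for exactly this pair: the denominator is small or zero.

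Percent change is also lopsided. It cannot fall below -100% but has no upper limit, which matters most for a marker expected to rise.

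At stake is how the apoptosis readout is interpreted. Section 2.5.2 treats the Part 1 biopsies as a measure of target inhibition at each dose level and hopes to relate the Part 2 biopsies to response and outcome. In groups this small, one lost pair is a third of a three-patient dose level, or a quarter of a cohort with four pairs.

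**Working it through.** The plan states no sample size, power or target for this endpoint, so there is no figure of its own to reproduce.

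**Inputs from the documents:** the percent scale, the markers, and 15 pairs in Part 2 (Sections 9.1.2.2, 13.4.1.3, 13.4.2.1 and 13.1.2.3). **Assumptions:** an H-score from 0 to 300, equal to 0 when no cell stains; every baseline value, zero-baseline share and reading error below.

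**1. The formula.** Percent change = 100 × (on-treatment - pre-treatment) / pre-treatment. For a 20-point rise:

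- from 20: 100 × 20/20 = +100%
- from 2: 100 × 20/2 = +1000%
- from 0: division by zero, no value

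**2. Sensitivity to reading error.** Take a true 10-point rise and a baseline misread by 2 points either way.

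- True baseline 5, on-treatment 15: 100 × (15 - 3)/3 = +400%, or 100 × (15 - 7)/7 = +114%.
- True baseline 100, on-treatment 110: 100 × (110 - 98)/98 = +12%, or 100 × (110 - 102)/102 = +8%.

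**3. Chance that at least one pair is undefined.** If a share q of baselines is zero, the chance among n pairs is 1 - (1 - q)^n.

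| Assumed q | n = 15 | n = 4 |
|---|---|---|
| 2% | 26% | not run |
| 5% | 54% | 18.5% |
| 10% | 79% | 34% |
| 20% | 96% | 59% |

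**4. Simulation.** 15 pairs, 20,000 replicates, gamma-distributed true baselines with SD 0.8 times the mean, reading-error SD 3, integer scores held within 0 to 300, true rise of 10 points.

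| Assumed mean baseline | Pairs undefined | Share of total rise lost | Median percent change, 95% range | Mean absolute change, 95% range |
|---|---|---|---|---|
| 5 | 17% | 21% | 85 to 350 | 7.7 to 11.8 |
| 10 | 8.1% | 10.1% | 54 to 200 | 7.7 to 12.0 |
| 30 | 1.9% | 2.4% | 21 to 72 | 7.8 to 12.1 |
| 150 | 0.2% | 0.2% | 4 to 15 | 6.5 to 11.5 |

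With no true change and a mean baseline of 5, the mean percent change centres near +11% (95% range -39 to +102), while the mean absolute change centres on 0 (-1.9 to 1.9).

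**5. Worked example of the remedy.** Take baselines 0, 0, 0, 1, 1, 2, 3, 4, 5, 6, 8, 10, 15, 20 and 30, each rising by 10. Percent change exists for 12 pairs, with mean 3825/12 = +319% and median (200 + 166.7)/2 = +183%. Absolute change exists for all 15, with mean and median +10. A log2 ratio with an added constant also keeps all 15, but its mean depends on the constant: 2.11 with 0.5, 1.83 with 1, 1.07 with 5.

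**The case against.** The strongest reply has five parts.

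- **Distortion is not shown.** A reader might infer that the apoptosis readout will be distorted. The documents do not support that: they give no baseline cleaved caspase-3 score, and the evidence in Section 2.4 is preclinical. At high baselines the effect is negligible, as step 4 shows.
- **No mean and no exclusion rule is planned.** A reader might also infer that one low-baseline pair will drive the Part 2 average, since a single +1000% pair adds 1000/15 = 67 points to a mean of 15. But the plan names no group mean and does not say that zero-baseline pairs are dropped. Section 9.1.2.2 describes a per-patient change, and the historical summary in Section 2.2.1.2 is a median.
- **The H-score is only an example.** The endpoint itself is a change in levels, so adding absolute change would not contradict it.
- **Percent change has a use.** Section 2.2.1.2 gives trametinib benchmarks of 62% inhibition of pERK and 83% of Ki67, and reports a rise in p27 on the same scale.
- **Little depends on it.** The readout is exploratory, and absolute change can be computed later from the same two values.

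All five stand as limits on the claim. They do not remove it. The sentence before the example applies percent change to any marker, and that rule has no answer for a zero baseline. A median tames an extreme pair but does not supply an undefined one. The benchmarks argue for keeping percent change for P-ERK and Ki67; Section 2.2.1.2 has none for cleaved caspase-3.

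**Conclusion.** The point holds as a minor one. The only stated reporting scale is undefined at a zero pre-treatment score and unstable near zero, and no fallback is given. For cleaved caspase-3 it can lose or distort pairs. Whether it will cannot be said: across the assumed mean baselines of 5 to 150, undefined pairs range from 17% down to 0.2%.

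The effect is confined to a small exploratory secondary readout: the first 15 patients in Part 2, possibly fewer usable pairs because biopsy depends on a safely accessible lesion, and 3 to 6 patients per dose level in Part 1. Neither the escalation rule in Table 5.3 nor the two-stage response rule in Section 13.1.2 uses it, so no primary endpoint, sample size or error rate changes. The conclusion assumes that a score of 0 is possible, as it is for a stain with no positive cells.

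**What to change.** Amend Sections 9.1.2.2, 13.4.1.3 and 13.4.2.1 together.

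- For every pair and marker, list the raw pre-treatment and on-treatment values. For markers not read by H-score, such as mRNAs, nothing more is asked here.
- For cleaved caspase-3, make the reported measure the absolute paired change in H-score (on-treatment minus pre-treatment), summarised by the median over all pairs, zero baselines included.
- For P-ERK and Ki67, keep percent change, so that the comparison with the Section 2.2.1.2 benchmarks survives, and show absolute change beside it so that zero-baseline pairs are retained.

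No significance test is needed to close this gap. Absolute change is simpler than an offset log ratio because no constant has to be chosen.

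The cost is wording plus one extra summary column; no new data are required. The drawback is that cleaved caspase-3 would have a different primary scale from the other two markers.

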13.4.2 Secondary Endpoints for Part 2 (Phase 2)

13.4.2.1 Pharmacodynamic Endpoints

Change in levels (between pre-treatment and post treatment tumor biopsies) of proteins/mRNAs

NCI Protocol #: 9525

Version Date: July 22, 2022

implicated in MAPK or BCL2 family signaling (e.g. phosphorylated ERK (P-ERK)), proliferation markers (Ki67), or apoptosis markers (Cleaved caspase-3) will be evaluated in paired tumor biopsies obtained. Results will be reported as a % increase or decrease in level of a given marker after treatment initiation (post treatment biopsy) relative to before treatment (pretreatment biopsy). For example, the % increase or decrease in the H-score of P-ERK, Ki67, or Cleaved caspase-3 will be reported relative to the pre-treatment biopsy.

13.5 Reporting and Exclusions

13.5.1 Evaluation of Toxicity

All patients will be evaluable for toxicity from the time of their first treatment with navitoclax and/or trametinib.

13.5.2 Evaluation of Response

All patients included in the study must be assessed for response to treatment, even if there are major protocol treatment deviations or if they are ineligible. Each patient will be assigned one of the following categories: 1) complete response, 2) partial response, 3) stable disease, 4) progressive disease, 5) early death from malignant disease, 6) early death from toxicity, 7) early death because of other cause, or 9) unknown (not assessable, insufficient data). [Note: By arbitrary convention, category 9 usually designates the "unknown" status of any type of data in a clinical database.]

All of the patients who met the eligibility criteria (with the possible exception of those who received no study medication) should be included in the main analysis of the response rate. Patients in response categories 4-9 should be considered to have a treatment failure (disease progression). Thus, an incorrect treatment schedule or drug administration does not result in exclusion from the analysis of the response rate. Precise definitions for categories 4-9 will be protocol specific.

All conclusions should be based on all eligible patients. Sub analyses may then be performed on the basis of a subset of patients, excluding those for whom major protocol deviations have been identified (*e.g.*, early death due to other reasons, early discontinuation of treatment, major protocol violations, etc.). However, these sub analyses may not serve as the basis for drawing conclusions concerning treatment efficacy, and the reasons for excluding patients from the analysis should be clearly reported. The 95% confidence intervals should also be provided.

REFERENCES

Balagula, Y., K. Barth Huston, K.J. Busam, *et al.* (2010). Dermatologic side effects associated with the MEK 1/2 inhibitor selumetinib (AZD6244, ARRY-142886). *Invest New Drugs*. 29:1114-1121.

Bekaii-Saab, T., M.A. Phelps, X. Li, *et al.* (2011). Multi-institutional phase II study of selumetinib in patients with metastatic biliary cancers. *J Clin Oncol.* 29:2357-2363.

Bendell, J., P. LoRusso, E. Kwak, *et al.* (2011). Clinical combination of the MEK inhibitor GDC-0973 and the PI3K inhibitor GDC-0941: A first-in-human phase Ib study in patients with advanced solid tumors. *AACR Meeting Abstracts*. Abstract LB-89.

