4. REGISTRATION PROCEDURES

4.1 General Guidelines

Dana Farber Harvard Cancer Center (DF/HCC) institutions (Massachusetts General Hospital and Dana Farber Cancer Institute) will register eligible participants with the DF/HCC Quality Assurance Office for Clinical Trials (QACT) central registration system. Registration must occur prior to the initiation of therapy. Any participant not registered to the protocol before treatment begins will be considered ineligible and registration will be denied.

A member of the study team will confirm eligibility criteria and complete the protocol-specific eligibility checklist.

Following registration, participants may begin protocol treatment. Issues that would cause treatment delays should be discussed with the Principal Investigator. If a participant does not receive protocol therapy following registration, the participant's protocol status must be changed. Notify the QACT Registrar of participant status changes as soon as possible.

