Patients will be enrolled to each expansion cohort according to the schema below. A total of 12 patients will be enrolled in each expansion cohort. If no objective tumor responses (partial or complete responses, as defined in section 11.1.4) are seen in the first 12 patients enrolled in a given cohort, the cohort will close. If at least one objective tumor response is observed in a given cohort, an additional 13 patients (for a total of 25 patients) will be enrolled to that cohort. Statistical considerations are discussed in more detail in Section 13. Patients will be assessed weekly for toxicity and safety during the first 28-day cycle and monthly thereafter. Patients will undergo radiographic assessment of tumor response every 2 cycles (8 weeks).

Part 2 (Phase 2)

Version Date: July 22, 2022

Stage 2:	Stage 2:	Stage 2:	Stage 2:
Enroll 13	Enroll 13	Enroll 13	Enroll
Patients	Patients	Patients	Patients
N = 25 total			

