10. STUDY CALENDAR

Baseline evaluations are to be conducted within 2 weeks prior to start of protocol therapy. Scans and x-rays, Echocardiogram or MUGA, and ophthalmic examination must be done ≤ 4 weeks prior to the start of therapy. In the event that the patient's condition is deteriorating, laboratory evaluations should be repeated within 48 hours prior to initiation of the next cycle of therapy. All study visits have a ± -3 day window after Cycle 2, Day 1.

Labs obtained on C1, D1 must re-meet eligibility criteria.

[#] Represents 14th day of trametinib dosing under Schedule C Trametinib dosing is always in the evenings. Timing is not adjusted on PK days

Part 1 (Phase 1b) Schedule A

	Pre- Study	C1D1	C1D7	C1D8	C1D15	C1D21	C1D22	C2D1	C2D15	C3D1, C4D1, etc	Off Study ^q
Trametinib				T	T	T	T	T	T	Т	
Navitoclax		L	L	N	N	N	N	N	N	N	
Informed consent a	X										
Demographics	X										
Medical history	X										
Concurrent meds	X	X								X	
Physical exam b	X	X		X	X		X	X	X	X	X
Vital signs c	X	X	X	X	X	X	X	X	X	X	X
Height	X										
Weight	X	X		X	X		X	X	X	X	X
Performance status	X	X		X	X		X	X	X	X	X
CBC w/diff, plts	X	X	X		X		X	X	X	X	X
Serum chemistry ^d	X	X	X		X		X	X	X	X	X
PT/PTT	X	X	X				X			X	X
Tumor Markers ^e	X							X		X	X
Urinalysis	X										
EKG ^f	X	X		X	X		X	X	X		
Echocardiogram or MUGA	X	Repeat	on C1D28				l.) Thereaft ine and foll			reeks (use	
Ophthalmology exam	X		Rej	peated as	needed onl	y if patient	experience	s vision cl	hanges		
Adverse event evaluation		X								X	X
Radiologic evaluation/Tumor measurements	X	Cycle 1	Radiologic measurements (by CT or MRI) should be performed every 8 weeks following Cycle 1 Day 1. Tumor measurements are repeated every 8 weeks. Documentation (radiologic) must be provided for patients removed from study for progressive disease. h								
B-HCG i	X										

92

Version Date: July 22, 2022

Tumor biopsy	X j				Xk			
PK blood draw ^l		Xm	Xm	X ⁿ	Xn	Xº	X^{l}	
Archival Tissue	Xp							

- T: Trametinib. Dose as assigned; dose first in morning on empty stomach, at least 1 hour before food (there are no hematologic paramaters that must be met to continue dosing with trametinib at the beginning of each cycle.)
- N: Navitoclax. Dose as assigned; dose second in morning with food, at least 1 hour after trametinib
- L: Lead-in dose of navitoclax. 150 mg daily in morning for 7 days, dosed as above.
- a: Informed consent can be signed within 28 days of C1D1.

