The primary goal of Part 2 is to evaluate the efficacy of this regimen in patients with various KRAS or NRAS mutation-positive solid tumor. Based on traditional response rates to standard second line chemotherapy in the tumor types being studied (Guglielmi et al, 2007; Conroy et al, 2011), we conclude that a response rate of 15-20% or greater in a given expansion cohort would deem this regimen worthy of further study in that specific patient population. In part 2, patients will be enrolled in 4 expansion cohorts by a two-stage design, as outlined in Section 5.1. Initially 12 patients will be enrolled to each cohort in Stage 1. If no responses are observed in a given cohort among the first 12 patients, then that cohort will be stopped for futility. However, if one or more responses are observed in a given cohort, the cohort will proceed to Stage 2, and an additional 13 patients will be enrolled for a total of 25 patients in that cohort. If at least three responses are observed within a completed cohort of 25 patients, the regimen will be considered promising for treating the specific tumor type. This design has a 11% false-positive and a 22% false-negative error rate for testing a 17% vs. a 5% response rate. The probability of early stopping is 54% if the underlying response rate were truly only 5%. In the event that the number of responses observed in a given cohort does not meet the pre-established response criteria defined above, but promising anti-tumor activity is observed (such as prolonged stable disease or tumor regressions that fall short of the RECIST cutoff for partial response), the possibility of further evaluating of this regimen in the specific patient population can be explored through a joint discussion between the investigators, pharmaceutical collaborators, and the NCI-CTEP.

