13.2.2 Part 2 (Phase 2)

Part 2 of the study will involve four expansion cohorts each enrolling a maximum of 25 patients. Each cohort will enroll a minimum of 12 patients, and will enroll an additional 13 patients (for 25 total patients) if at least one objective tumor response is observed among the first 12 patients (as described above). Therefore, a minimum of 48 patients and a maximum of 100 patients will be enrolled to this part of the study. Based on past accrual rates at DF/HCC for patients with KRAS or NRAS mutation-positive solid tumors, we estimate that between 8-10 patients will be enrolled per month to the phase 2 portion of the study, resulting in an anticipated maximum accrual time of 10-12 months.

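### Do the Part 2 response counts rest on enrolled or eligible patients, and could the two give different decisions?

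*Combined protocol and SAP*

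**What the plan says.** The decision rule appears in three places, each time in terms of enrolment. Section 5.1.2 says that if no objective responses "are seen in the first 12 patients enrolled in a given cohort, the cohort will close". Section 13.1.2 repeats the stage 1 stop and adds 13 patients after one or more responses. It then says: "If at least three responses are observed within a completed cohort of 25 patients, the regimen will be considered promising". Section 13.2.2 describes "four expansion cohorts each enrolling a maximum of 25 patients". Section 13.1.2 gives the operating characteristics for response rates of 5% and 17%: 11% false-positive, 22% false-negative, and 54% early stopping at 5%.

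Section 13.5.2 covers the analysis of response. Every patient is to be assessed, "even if there are major protocol treatment deviations or if they are ineligible". The main response-rate analysis takes those who met the eligibility criteria, "with the possible exception of those who received no study medication", and counts categories 4 to 9 as failures. It then states "All conclusions should be based on all eligible patients" and asks for 95% confidence intervals.

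Two other places bear on who is in each set. Section 10 requires "Labs obtained on C1, D1 must re-meet eligibility criteria". Section 4.1 provides for a change of status "If a participant does not receive protocol therapy following registration". Part 2 has no replacement rule; replacement is stated only for patients not evaluable for dose-limiting toxicity in Part 1.

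**The concern.** Calling a regimen promising is a conclusion about efficacy. Read literally, Section 13.5.2 would have it rest on eligible patients, while Section 13.1.2 counts 25 enrolled patients. Because ineligible patients are still assessed for response, an ineligible responder can exist in the data.

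Small cohorts make this look serious, since a single patient can sit on the boundary:

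- One responder in 12 who is ineligible leaves 0 of 11 eligible.
- Three responders in 25, one of them ineligible, leave 2 of 24.

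If the set were chosen after the responses were known, that would be a post hoc choice on the primary endpoint. The loose wording on never-treated patients adds a second question: whether they fill places among the 12 and the 25.

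**Working it through.** **1. The plan's own figures.** Inputs from Section 13.1.2: 12 then 13 patients, continue with at least 1 response, promising with at least 3 of 25, rates 5% and 17%. Let X be the responses in the first 12 and Y those in the next 13.

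P(early stop) = (1 − p)^12 = 0.95^12 = 0.5404 at 5%.

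P(promising) = P(X=1)·P(Y≥2) + P(X=2)·P(Y≥1) + P(X≥3)

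- At 5%: 0.3413 × 0.1354 + 0.0988 × 0.4867 + 0.0196 = 0.0462 + 0.0481 + 0.0196 = 0.1139.
- At 17%: 0.2627 × 0.6751 + 0.2960 × 0.9113 + 0.3344 = 0.1774 + 0.2697 + 0.3344 = 0.7815, so the false-negative rate is 0.2185.

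These match the stated 54%, 11% and 22%. The published error rates therefore belong to a count of all 12 and all 25 patients.

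**2. How often one patient is decisive.** Exactly 1 response in 12 has probability 0.3413 at 5% and 0.2627 at 17%. Exactly 3 of 25, having passed stage 1, has probability 0.0814 at 5% and 0.1641 at 17%. Boundary results are common, so the question is how often a boundary responder would be ineligible.

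**3. How often the final verdict would differ.** The documents give no ineligibility rate. Assume each patient is ineligible with probability q, independently of response, and apply the same cut-offs to eligible responders. Applying those cut-offs to eligible patients is itself an assumption, because Section 13.5.2 does not do so. Exact enumeration of eligible responders, ineligible responders and non-responders over both stages gives:

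| q | Either step differs, 5% | Final verdict differs, 5% | Either step differs, 17% | Final verdict differs, 17% |
|---|---|---|---|---|
| 2% | 1.1% | 0.5% | 1.4% | 1.2% |
| 4% | 2.2% | 1.0% | 2.8% | 2.5% |
| 12% | 6.5% | 2.9% | 9.1% | 8.1% |

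A hand check at q = 2%: the main term is exactly three responders with at least one ineligible, 0.0814 × (1 − 0.98^3) = 0.0814 × 0.0588 = 0.0048 at 5%, and 0.1641 × 0.0588 = 0.0096 at 17%. Rarer paths make up the rest.

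At 5%, more than half of the either-step figure comes from stage 1 alone, where both counts end without a promising verdict (at q = 4%, 2.2% − 1.0% = 1.2%). A q of 12% means 3 of 25 patients in a cohort, which is hard to square with eligibility being validated at registration.

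**4. What each choice would cost.** Counting eligible patients only, with cut-offs unchanged:

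- One ineligible patient in stage 1 (11, then 24): false-positive 10.2%, false-negative 24.9%.
- One in stage 2 (12, then 24): 10.5% and 23.6%.

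Keeping never-treated patients in the 12 and 25 as non-responses without replacement, with 17% as the rate among treated patients (an assumption):

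- Two never treated, one per stage (11, then 23 treated): false-negative 26.8%.
- Three, two of them in stage 1 (10, then 22 treated): 30.4%.

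**5. What Section 13.5.2 would report at the boundary.** 2 of 24 is 8.3%, with exact 95% interval 1.0% to 27.0%. That interval contains both 5% and 17%, so it is an imprecise estimate and not a contrary verdict.

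**The case for a change.** The strongest case for a change is that the texts do differ, that the published error rates fit only the enrolled count, and that a few sentences would settle it. If the eligible reading governs the final verdict, stage 1 and the final decision use different sets, and no cut-off is given for fewer than 25. Section 13.1.2 sends Part 2 response evaluation to Section 11 alone, whereas the Part 1 text in Section 13.4.1.2 names both Section 11 and Section 13.5.2. Section 11.1.1 adds an evaluable set whose role is not stated. Late ineligibility has a possible route, because Section 9.1.1.1 allows enrolment before central confirmation of the mutation.

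The missing cross-reference is real, and so is the vague wording on never-treated patients. The rest carries less weight:

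- Opening stage 2 is an accrual step, not a conclusion, and Section 13.5.2 does not speak to it.
- Section 13.5.2 sets the population for the rate and its interval. It does not restate the three-response cut-off on a smaller number.
- Section 4.2 requires every criterion to be met, and the registrar validates eligibility before registration. Section 3.1.1 asks only for a mutation result from a CLIA-certified laboratory, so a failed central check does not clearly make a patient ineligible.
- A patient who fails the day 1 laboratory check would not be expected to start treatment, and a never-treated patient cannot respond to it. Neither produces an ineligible responder.
- Section 13.5.2 counts unassessable patients as failures and bars subset analyses from supporting efficacy conclusions, so the Section 11.1.1 set cannot displace the main analysis.
- Section 13.1.2 lets a cohort that misses the criteria still be considered further by joint discussion, which softens a one-patient miss.

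**Conclusion.** The concern does not call for a change. The plan leaves unwritten which set governs in a rare case, and a statistician would settle that without difficulty: run the two stages on the patients enrolled, as the rule and its error rates are written, and report the response rate and interval in eligible patients, as Section 13.5.2 asks. A discrepancy at a boundary would be visible in that report.

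Fixing one set in advance is also no clear gain. Counting all enrolled patients keeps the stated error rates but lets an ineligible responder count towards a promising verdict. Counting eligible patients only respects Section 13.5.2 but moves the false-negative rate from 22% to roughly 24% or 25% for each ineligible patient. Keeping never-treated patients as unreplaced non-responses would raise it to 27% with two and 30% with three.

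The final verdict would differ in about 0.5% to 1.2% of cohorts at 2% ineligibility and 1.0% to 2.5% at 4%, the lower figure applying at a true rate of 5% and the higher at 17%. These figures assume that ineligibility is independent of response and that the same cut-offs apply to both sets. A much higher ineligibility rate would enlarge them (2.9% and 8.1% at 12%), but nothing in the documents points to one.
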